10.4.4 Instructions for reporting serious adverse events

- In the case of occurrence of an SAE, the Investigator or any designees must immediately:
 - ENTER (within 24 hours) the information related to the SAE in the appropriate screens of the e-CRF; the system will automatically send a notification to the

monitoring team after approval of the Investigator within the e-CRF or after a standard delay,

- SEND (preferably by fax or e-mail) a photocopy of all examinations carried out and the dates on which these examinations were performed, to the representative of the monitoring team whose name, fax number, and email address appear on the Clinical Trial Protocol. Care should be taken to ensure that the patient's identity is protected and the patient's identifiers in the clinical trial are properly mentioned on any copy of a source document provided to the Sponsor. For laboratory results, include the laboratory normal ranges,
- All further data updates should be recorded in the e-CRF as appropriate, and further documentation as well as additional information (for laboratory data, concomitant medications, patient status, etc.) should be sent (by fax or e-mail) to the monitoring team within 24 hours of knowledge of the SAE. In addition, every effort should be made to further document any SAE that is fatal or life threatening within a week (7 days) of the initial notification,
- A back-up plan (using a paper CRF process) is available and should be used when the e-CRF system does not work.
- Any SAE brought to the attention of the Investigator at any time after the end of the study for the patient and considered by him/her to be caused by the IMP with a reasonable possibility, should be reported to the monitoring team.

10.4.5 Guidelines for reporting adverse events of special interest

For AESIs, the Sponsor must be informed immediately (ie, within 24 hours), as per SAE notification guidelines described in Section 10.4.4, even if not fulfilling a seriousness criterion, using the corresponding pages of the CRF (to be sent) or screens in the e-CRF.

10.4.5.1 Reporting of adverse events of special interest with immediate notification

For AESIs with immediate notification, the Sponsor will be informed immediately (ie, within 24 hours), as per the SAE notification instructions described in Section 10.4.4, even if not fulfilling a seriousness criterion, using the corresponding pages in the CRF (to be sent) or screens in the e-CRF.

10.4.5.2 Reporting of adverse events of special interest without immediate notification

Asymptomatic overdose (accidental or intentional) with the IMP/NIMP is defined as any "significant" overdose, without clinical symptoms and/or signs, either suspected by the Investigator or spontaneously notified by the patient (not based on accountability assessment). It will be recorded as an AE "Asymptomatic OVERDOSE (accidental or intentional)".

10.4.6 Guidelines for management of specific laboratory abnormalities

Decision trees for the management of certain laboratory abnormalities by Sanofi are provided in Appendix B.

Property of the Sanofi Group - strictly confidential

The following laboratory abnormalities should be monitored, documented, and managed according to the related flow chart in protocol appendices:

- Neutropenia.
- Thrombocytopenia.
- Increase in ALT.
- Acute renal insufficiency.
- Suspicion of rhabdomyolysis.

Table 1 - Summary of adverse event reporting instructions

Event category	Reporting timeframe	Specific events in this category	Case Report Form completion		
			AE form	Safety Complementary Form	Other specific forms
Adverse event (non-SAE, non-AESI)	Routine	Any AE that is not SAE or AESI	Yes	No	No
Adverse event	Routine	Allergic or allergic-like	Yes	No	Yes
Serious adverse event (non-AESI or AESI)	Expedited (within 24 hours)	Any AE meeting seriousness criterion per Section 10.4.1.2	Yes	Yes	No
Adverse event of special interest	Expedited (within 24 hours)	Pregnancy	Yes	No	Yes
		Symptomatic overdose with IMP/NIMP	Yes	Yes	No
		ALT ≥3 x ULN or ALT >2 x baseline if baseline ALT ≥ULN	Yes	Yes	Yes

10.5 OBLIGATIONS OF THE SPONSOR

During the course of the study, the Sponsor will report in an expedited manner:

- All SAEs that are both unexpected and at least reasonably related to the IMP (suspected unexpected serious adverse reaction [SUSAR]), to the health authorities, Independent Ethics Committees (IECs)/Institutional Review Boards (IRBs) as appropriate and to the Investigators.
- All SAEs that are both expected and at least reasonably related to the IMPs to the health authorities, according to local regulations.
- The following AESIs to the Health Authorities
 - Pregnancy,
 - Symptomatic overdose with IMP/NIMP,
 - ALT >3 x ULN or ALT >2 x baseline if baseline ALT \geq ULN.

Adverse events that are considered expected will be specified by the reference safety information (Investigator's Brochure).

As this is an open label study, no un-blinding of SUSARs is necessary.

The Sponsor will report all safety observations made during the conduct of the trial in the CSR.

10.6 SAFETY INSTRUCTIONS

10.6.1 Hypoglycemia

Severe symptomatic hypoglycemia

- Severe symptomatic hypoglycemia is an event requiring assistance of another person to actively administer carbohydrate, glucagon, or other resuscitative actions. These episodes may be associated with sufficient neuroglycopenia to induce seizure, unconsciousness or coma. Plasma glucose measurements may not be available during such an event, but neurological recovery attributable to the restoration of plasma glucose to normal is considered sufficient evidence that the event was induced by a low plasma glucose concentration.
- The definition of severe symptomatic hypoglycemia includes all episodes in which neurological impairment was severe enough to prevent self-treatment and which were thus thought to place patients at risk for injury to themselves or others.
- Note that "requires assistance" means that the patient could not help himself or herself. Assisting a patient out of kindness, when assistance is not required, should not be considered a "requires assistance" incident.
- Severe symptomatic hypoglycemia will be qualified as an SAE only if it fulfills SAE criteria. All events of seizure, unconsciousness or coma must be reported as SAEs.
- If a participant reports a severe hypoglycemia between the on-site visits or during a phone call visit, the Investigator should ask him/her to come to the study site on the same or the next day, so that the event can be properly assessed and reported.

For description of all other hypoglycemia event types and discussion of endpoints related to hypoglycemia, see Section 9.2.3.2.1.

10.6.2 Injection site reactions

In case the Investigator or the patient recognizes any sign related to local non-allergic reactions at the study drug injection site (Section 9.2.3.2.4), this should be recorded on the AE page in the e-CRF.

10.6.3 Hypersensitivity reactions

In case a patient experiences an event identified as a potential hypersensitivity reaction (an allergic reaction or an allergic-like reaction), this has to be reported as an AE and recorded in the e-CRF on the AE page; additional information is collected on the specific allergic reaction complementary forms. Allergic reaction or possible allergic reaction will be adjudicated by the ARAC (Section 6.4).

If a participant reports a hypersensitivity reaction between the on-site visits or during a phone call visit, it is recommended that the Investigator ask him/her to come to the study site on the same or the next day as clinically appropriate, so that the event can be properly assessed and reported.

Virtually all symptoms listed on the allergic reaction complementary form are possible adverse reactions that may be allergic in nature and may need to be addressed after medical judgment, excluding another etiology than allergy.

Sometimes transient injection site reactions, irritant in nature may occur requiring no intervention and are of dubious significance. These reactions would not be considered to be allergic reactions. Adverse events that are obviously not of allergic origin (eg, local injection site reactions) should not be recorded on the Allergic Reaction Complementary Form.

10.6.4 SMPG

Safety instructions are provided for SMPG in Section 9.2.2.2.3 and Section 9.2.3.2.1.1.

10.6.5 Follow-up of laboratory abnormalities

Decision trees for the management of certain laboratory abnormalities are provided in Section 17, Appendix B. Assessment of General Safety Laboratory data is provided in Section 9.2.3.2.3.

In subjects in whom the ARAC assesses AIA-mediated hypersensitivity reaction or insulin resistance, the increased AIA titers will be followed until return to baseline or until ARAC decides that no further follow-up is deemed necessary.

10.6.6 Other

Assessment of vital signs is noted in Section 9.2.3.2.5 and of ECG in Section 9.2.3.2.7.

10.7 ADVERSE EVENTS MONITORING

All events will be managed and reported in compliance with all applicable regulations, and included in the final CSR.

11 STATISTICAL CONSIDERATIONS

11.1 DETERMINATION OF SAMPLE SIZE

The sample size calculations are performed based on the primary endpoint, change in HbA1c from baseline to Week 26 (in %).

A sample size of 580 patients (290 patients per arm; approximately 480 T1DM patients [230 patients in the US using NovoLog and 250 patients in countries using NovoRapid] and 100 T2DM patients [all in the US using NovoLog]) will ensure that the upper bound of the 2-sided 95% confidence interval (CI) for the adjusted mean difference between SAR341402 and NovoLog/NovoRapid would not exceed a non-inferiority margin of 0.3% HbA1c with at least 95% power. This sample size will also ensure that the lower bound of this 2-sided 95% CI would not be below -0.3% HbA1c with at least 95% power, thus will provide at least 90% power to show both non-inferiority of SAR341402 over NovoLog/NovoRapid (primary analysis) and inverse non-inferiority of NovoLog/NovoRapid over SAR341402 (secondary analysis). These calculations assume a common standard deviation (SD) of 1.0% and a true difference in HbA1c between the treatment groups of zero.

An exploratory analysis of the percentage of patients with treatment-emergent AIAs (AIA incidence) will be performed to compare the immunogenicity of SAR341402 versus NovoLog/NovoRapid. The sample size of 580 patients would ensure that the 2-sided 90% CI for the adjusted risk difference between SAR341402 and NovoLog/NovoRapid would be included within the [-10%; 10%] interval with at least 68% power. This calculation assumes a true risk difference between the treatment groups of zero and a maximum AIA incidence of 30% (in previous Sanofi clinical studies performed with rapid-acting insulin analogs, AIA incidence in the range of 15-20% were observed at 6 months). The power calculations are presented in Table 2.

Table 2 - Power calculation based on the percentage of patients with treatment-emergent AIAs

Percentage of patients with treatment-emergent AIAs	10%	20%	30%
Power for N=580 (290/arm)	97%	82%	68%

To reach this number of 580 patients randomized for the 6-month comparative efficacy and safety period, calculations were made using the nQuery Advisor® Software Version 7.0.

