11.3.3 Anti-insulin antibody population

The AIA population is defined as all patients from the safety population with at least one AIA sample available for analysis (sample collected at least 8 hours after the last administration of mealtime insulin) during the on-treatment period, analyzed according to the treatment actually received.

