1.3 DETERMINATION OF SAMPLE SIZE

The sample size calculation was performed based on the primary endpoint, change in HbA1c (%) from baseline to Week 26.

A sample size of 580 patients (290 patients per arm; approximately 480 T1DM patients [230 patients in the US using NovoLog and 250 patients in countries using NovoRapid] and 100 T2DM patients [all in the US using NovoLog]) will ensure that the upper bound of the 2-sided 95% confidence interval (CI) for the adjusted mean difference between SAR341402 and NovoLog/NovoRapid would not exceed a non-inferiority margin of 0.3% HbA1c with at least 95% power. This sample size will also ensure that the lower bound of this 2-sided 95% CI would not be below -0.3% HbA1c with at least 95% power, thus will provide at least 90% power to show both non-inferiority of SAR341402 over NovoLog/NovoRapid (primary analysis) and inverse non-inferiority of NovoLog/NovoRapid over SAR341402 (secondary analysis).

These calculations assume a common standard deviation (SD) of 1.0% and a true difference in HbA1c between the treatment groups of zero.

The non-inferiority margin of 0.3% HbA1c for the adjusted mean difference between SAR341402 and NovoLog/NovoRapid was chosen, as it is in line with recommendations by regulatory agencies including FDA, referring to a range of 0.3% to 0.4% (1), and the European Medicines Agency, suggesting the more stringent non-inferiority margin of 0.3% (2), and based on historical precedent for comparative insulin studies in which a 0.3% non-inferiority margin is often used.

An exploratory analysis of the percentage of patients with treatment-emergent AIAs (AIA incidence) will be performed to compare the immunogenicity of SAR341402 versus NovoLog/NovoRapid. The sample size of 580 patients would ensure that the 2-sided 90% CI for the adjusted risk difference between SAR341402 and NovoLog/NovoRapid would be included within the [-10%; 10%] interval with at least 68% power. This calculation assumes a true risk difference between the treatment groups of zero and a maximum AIA incidence of 30% (in previous Sanofi clinical studies performed with rapid-acting insulin analogs, AIA incidence in the range of 15-20% were observed at 6 months). The power calculations are presented in Table 1 below.

Table 1 - Power	calculation based	d on the percenta	ge of patients with	treatment-emergent AIAs
			3	

Percentage of patients with treatment-emergent AIAs	10%	20%	30%
Power for N=580 (290/arm)	97%	82%	68%

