2.4.4 Analyses of efficacy endpoints

2.4.4.1 Analysis of primary efficacy endpoint(s)

2.4.4.1.1 Primary efficacy analysis

First step analysis:

The statistical test for non-inferiority assessment of SAR341402 versus NovoLog/NovoRapid on the primary efficacy endpoint (change in HbA1c from baseline to Week 26 as defined in the Section 2.1.3.1) will be one-sided, with alpha level of 0.025 and using a non-inferiority margin of 0.3% HbA1c.

The primary endpoint will be analyzed in the ITT population using all post-baseline data available during the main 6-month randomized period (ITT estimand).

The analysis for change in HbA1c should account for missing data in a fashion consistent with what the measurement would have been, had it been measured. The behavior of missing data for those patients who are off-treatment may not be the same as that of observed data for those patients who are on-treatment in the same treatment arm. Therefore, it may not be appropriate to represent the missing data from patients who do not adhere to therapy by the data from those patients on the same arm who adhere to therapy.

Statistical Analysis Plan SAR314102-EFC15081 - insulin aspart 28-Feb-2018 Version number: 1

As a consequence, a multiple imputation approach will be used where missing data from patients who do not adhere to IMP will be represented by the data from those patients in the same treatment group who also do not adhere to IMP but have the measurement for the primary endpoint. Imputations will be performed with the MI procedure in SAS (Statistical Analysis System). Details of the proposed multiple imputation analysis in two parallel parts (according the status of the patients), are provided below:

Part1: Imputation for missing data in patients who prematurely discontinued IMP during the main 6-month randomized period:

Missing data in patients who prematurely discontinued IMP during the main 6-month randomized period will be imputed using a model estimated solely from data observed in other patients who discontinued IMP during the main 6-month randomized period but have the measurement for the primary endpoint at Week 26. Due to the anticipated small number of these latter patients, a basic imputation model will be built, including only the randomized treatment group as predictor. Missing data will be imputed using the regression method.

Part2: Imputation for missing data in patients who completed the main 6-month treatment period:

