Missing data in patients who completed the main 6-month treatment period will be imputed separately, using a model estimated solely from data observed in other patients who completed the main 6-month treatment period and have the measurement for the primary endpoint at Week 26. Since in general, the missing pattern will not be monotone, a two-step approach will be used:

- Step 1: the Markov Chain Monte Carlo (MCMC) method will be used in conjunction with the IMPUTE=MONOTONE option to create an imputed data set with a monotone missing pattern. The imputation model will include the continuous fixed covariates of the baseline HbA1c value as well as the changes from baseline in HbA1c at Week 12 and Week 26.
- Step 2: using the monotone data set from step 1, missing data will be imputed using the regression method. The imputation model will include the fixed categorical effects of the treatment group, the randomization strata of geographical region and type of diabetes (Europe T1DM, US T1DM, US T2DM, Japan T1DM) and prior use of NovoLog/NovoRapid (Yes, No), as well as the continuous fixed covariates of the baseline HbA1c value and the changes from baseline in HbA1c at Week 12 and Week 26.

Missing values will be imputed 10,000 times. Completed datasets from the two parts detailed above will be combined into a single dataset. Each completed dataset will be analyzed using an analysis of covariance (ANCOVA) of the change in HbA1c from baseline to Week 26, including the fixed categorical effects of treatment group (SAR341402, NovoLog/NovoRapid), the randomization strata of geographical region and type of diabetes (Europe T1DM, US T1DM, US T2DM, Japan T1DM) and prior use of NovoLog/NovoRapid (Yes, No), as well as the continuous fixed covariate of baseline value. Results from the 10,000 analyses will be combined using Rubin's formula (MIANALYZE procedure in SAS).

Statistical Analysis Plan SAR314102-EFC15081 - insulin aspart 28-Feb-2018 Version number: 1

The adjusted least squares (LS) mean of the change in HbA1c from baseline to Week 26 for each treatment group (SAR341402, NovoLog/NovoRapid) will be estimated, as well as the between-group LS mean difference of SAR341402 versus NovoLog/NovoRapid, with the corresponding standard errors and 2-sided 95% CIs. These values will be calculated using the observed proportions of patients in the randomization strata and the observed baseline mean HbA1c in the ITT population.

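### Do the stated powers (95% and 90% for HbA1c, 68% for antibodies) need restating because they allow for no missing data and leave the SD undefined?

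*Protocol*

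**What the plan says.** Protocol 11.1, the protocol synopsis and SAP 1.3 carry the same calculation. With 290 patients per arm, the upper limit of the two-sided 95% CI for the adjusted difference "would not exceed a non-inferiority margin of 0.3% HbA1c with at least 95% power". The same power is claimed for the lower limit against -0.3%, and the text concludes that this "thus will provide at least 90% power to show both non-inferiority of SAR341402 over NovoLog/NovoRapid (primary analysis) and inverse non-inferiority". The inputs are stated: "These calculations assume a common standard deviation (SD) of 1.0% and a true difference in HbA1c between the treatment groups of zero". Protocol 11.1 and SAP 1.3 describe the 580 as patients randomized.

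For treatment-emergent anti-insulin antibodies (AIA), the two-sided 90% CI for the risk difference "would be included within the [-10%; 10%] interval with at least 68% power", at an incidence taken as a maximum of 30%. The table gives 97%, 82% and 68% at incidences of 10%, 20% and 30%, and its row label shows 290 per arm.

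The analysis expects some data to be missing. SAP 2.4.4.1.1 keeps all randomized patients by multiple imputation. For patients who stopped study treatment and have no Week 26 value, the donors are patients who also stopped but were measured: "Due to the anticipated small number of these latter patients, a basic imputation model will be built". The antibody population (Protocol 11.3.3) needs one valid on-treatment sample per patient, and SAP 2.4.5.7 leaves inconclusive patients out of the risk-difference model.

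**The concern.** The power statements are worded as minimum values for the number randomized, and the calculation has almost no slack. No rate of missing or non-evaluable data is given, and no inflation step is shown. A reader could take 95% and 90% as guaranteed for 580 randomized patients when they are the values for complete data.

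The SD adds to the doubt. The CI concerns an adjusted difference from an ANCOVA, yet 1.0% is labelled neither as the raw SD of the change nor as the residual SD. One reading leaves room for missing data and the other leaves none. The power for both directions matters because the equivalence statement in Protocol 11.4.2.1.1 and SAP 2.4.4.1.1 rests on meeting both limits.

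**Working it through.** **Inputs from the documents.** Margin 0.3%, one-sided alpha 0.025, SD 1.0%, true difference 0, and 290 per arm (Protocol 11.1 and 11.4.2.1.1). For AIA: limits of ±10 percentage points, a 90% CI, true difference 0. The documents give no loss rate and no share of variance explained by covariates (R²), so those below are assumptions.

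**1. The plan's HbA1c figures.** SE = SD × √(2/n); power = Φ(0.3/SE − 1.96); power for both limits = 2 × power − 1.

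- n = 290: SE = √(2/290) = 0.08305; 0.3/0.08305 = 3.6125; Φ(1.6525) = 95.08%; both limits 90.16%. With the t distribution: 95.02% and 90.03%.
- n = 289: 95.01% and 90.03% (normal); 94.95% and 89.90% (t).

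The stated figures are right for the stated inputs, with a slack of none or one patient per arm.

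**2. Loss of information if 1.0% is the residual SD.**

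| Contributing per arm | Non-inferiority | Both limits |
|---|---|---|
| 290 | 95.1% | 90.2% |
| 275 (about 5% loss) | 94.0% | 88.1% |
| 261 (10% loss) | 92.9% | 85.8% |

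**3. The same loss if 1.0% is the raw SD of the change.** Residual SD = √(1 − R²).

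- 275 per arm, R² = 0.05: SD = 0.9747; power 95.0% and 90.1%.
- 261 per arm, R² = 0.10: SD = 0.9487; power 95.1% and 90.2%.

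Such R² values are modest, because baseline HbA1c is a covariate and the outcome is change from baseline. If the SD of the change is 1.0 and HbA1c has the same SD, s, at baseline and Week 26 (assumed), the correlation of change with baseline is −1/(2s), so R² = 0.25/s². For s between 1.0 and 0.7 that is 0.25 to 0.51. R² would be lower if the spread at Week 26 clearly exceeded that at baseline.

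**4. The imputation as planned.** Suppose a share d of each arm stops treatment and a share m of those is measured at Week 26. Filling the gaps from the measured stoppers multiplies the variance of the arm mean by (1 − d) + d/m, so the effective n is 290/[(1 − d) + d/m].

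- d = 5%, m = 50%: 290/1.05 = 276. Power 94.1% and 88.3%.
- d = 10%, m = 50%: 290/1.10 = 264. Power 93.1% and 86.2%.
- d = 5%, m = 80%: 290/1.0125 = 286. Power 94.8% and 89.7%.
- d = 10%, m = 80%: 290/1.025 = 283. Power 94.6% and 89.2%.

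These values take 1.0% as the residual SD. Simulating the regression imputation with Rubin's rules adds the cost of having few donors: about 93% and 87% in the first case, 92.5% and 85% in the second, 94.7% and 89.5% in the third, and 94.4% and 88.8% in the fourth. With 1.0% as the raw SD and R² = 0.10, the simulated second case is 94.5% and 89.3%, and the fourth is 96.3% and 92.8%.

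**5. AIA.** Power = 2Φ(0.10/√(2p(1 − p)/290) − 1.645) − 1. For p = 0.30: SE = 0.03806, 0.10/SE = 2.628, Φ(0.983) = 0.837, power 67.4%. For p = 0.10 and 0.20 it is 98.2% and 82.8%. Exact enumeration gives 98.1%, 82.9% and 67.5%. The plan's 97%, 82% and 68% agree to within two points, a difference of method.

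With 275 and 261 evaluable per arm (exact): 63.7% and 60.5% at 30% incidence, 80.1% and 77.5% at 20%, and 89.8% and 87.9% at 15%. Power stays at 68% or more up to an incidence of about 27% with 275 per arm and 25% with 261.

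**The case for a change.** The strongest case for a change is that slack of at most one patient per arm makes a stated minimum fragile, and that one undefined word, SD, decides whether it holds. SAP 1.5 records that the sample size was raised from 500 to 580 partly to increase power for both HbA1c tests. By the same formula 250 per arm gives 91.8% and 83.7%. If 1.0% is the residual SD, a 10% loss would therefore cancel about two-thirds of that gain: (95.1 − 92.9)/(95.1 − 91.8) = 2.2/3.3. Imputation keeps patients in the analysis but does not recover the information lost, and the AIA exclusions remove patients outright.

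The omission is real: neither document states full evaluability or defines the SD. The rest is weaker.

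- The powers are conditional on stated assumptions, and both the 290 per arm and the absence of inflation are visible in the text.
- Patients who stop treatment are kept in follow-up to at least Week 26 (Protocol 10.1.2 and 10.3.4, SAP 1.4), so measuring only half of them is pessimistic. Treatment completers have by definition attended Visit 9 (Protocol 11.2). The re-allocation of end-of-treatment assessments in SAP 2.5.4 also fills some Week 26 values.
- One valid AIA sample is enough, and sampling is scheduled at Weeks 4, 12 and 26, then 40 and 52 (Protocol 9.2.1.2). Nothing in the documents points to 5% to 10% exclusion.
- In the AIA sentence the minimum is taken over incidence: "This calculation assumes a true risk difference between the treatment groups of zero and a maximum AIA incidence of 30" per cent. It is not a promise about data loss. Deleting the qualifier would leave a flat 68% that conflicts with the table at 10% and 20%.

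**Conclusion.** No change is needed. The powers are correctly calculated, and what is missing is a description of the assumptions behind them. For HbA1c, the cost of 5% to 10% loss lies between nil and about 2 points for non-inferiority and 4 to 5 points for both limits. It is nil if 1.0% is the raw SD and covariates explain about 5% to 10% of the variance. It reaches the upper end only if 1.0% is already the residual SD and the loss is near 10%. Even then power is about 93% and 86%.

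For AIA, the 68% is at risk only near 30% incidence. At the 15-20% that the protocol cites from earlier studies, power stays at 77% or more with 261 evaluable per arm, and the comparison is exploratory without formal testing.

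The margin, the ANCOVA, the imputation and the criteria for non-inferiority and equivalence do not use the power figures. Loss of precision appears as a wider CI, which the decision rule already takes into account. Restating the figures would mean amending the protocol of a trial that, by SAP 1.5, began randomizing on 14-Aug-2017, with ethics approval under Protocol 15, and it would alter no result. A sponsor revising the section for other reasons could add a sentence on evaluable numbers and the meaning of the SD.
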